#### 8.1.2 Serious Adverse Events

A serious adverse event is defined as any untoward event that is:

- Fatal;
- Life-threatening; (ie. the subject is at immediate risk of death, not at risk only if the event worsens or fails to respond to intervention)
- Results in persistent or significant disability/incapacity;
- Medically significant;
- Causes a congenital abnormality or birth defect;
- Requires or prolongs inpatient hospitalization.

Investigator judgment must be used to assess an event as medically significant. The event may not be life-threatening or cause disability but may jeopardize the subject and require intervention to prevent the other SAE outcomes.

The following situations should not be reported as an SAE:

- Death due to disease progression;
- Hospitalization for signs and symptoms associated with disease progression;
- Hospital admission not associated with a precipitating AE such as:
  - Treatment for a preexisting condition not associated with a new AE or the worsening of a preexisting condition;
  - Admission for social or administrative reasons;
  - Optional admission or elective surgery;
  - Observation;
  - Preplanned treatments or surgical procedures as noted at baseline;
  - Admission for the administration of blood products.

#### 8.2 Adverse Event Reporting

The investigator and qualified designees are responsible for the detection, documentation, reporting, and follow-up of all adverse events experienced by subjects during trial participation. AEs and SAEs will be recorded from the initiation of study therapy until 28 days after the last dose of study medication or until new cancer therapy is started. The following information will be required for each adverse event:

- Event term;
- For non-hematologic toxicities and patients with normal baseline platelet, hemoglobin and ANC, event severity as graded by the CTCAE v.5;
- For patients with baseline cytopenias (i.e. platelet count <100,000/mm^3 and/or hemoglobin less than the lower limit of normal), hematologic toxicity event severity as graded by 2018 iwCLL criteria (Refer to section 6.6.3)
- The causality assessment to study medication per the below definitions;
- Expectedness;
- Event duration;
- Any action taken to treat or manage the event;
- Event outcome.

# 8.2.1 Severity Assessment

The severity of adverse events should be assessed by CTCAE v.5. If an event is not listed in CTCAE v.5 then the assessment of severity should follow the general guidelines listed in Table 18.

#### Table 18: Severity assessment

Grade	Severity Description
1	Mild event that generally does not require intervention.
2	Moderate event that may require intervention.
3	Severe event that requires intervention.
4	Life-threatening event that requires urgent intervention.
5	Death.

Events meeting grade 4 or 5 severity description should be reported promptly as SAEs unless otherwise indicated in Section 8.1.

#### 8.2.2 Causality Assessment

The Investigator should assess the causality or relationship of AEs and SAEs to study therapy. The Investigator should consider if there is evidence that the investigational product caused the event taking into consideration timing, organ system affected, type of event, and possible alternative etiologies. The relationship of the AE to study treatment will be reported as listed below. These categories will be defined as follows:

- Definitely related (D) a clinical event, including laboratory test abnormality, occurring in a plausible time relationship to drug administration, and which cannot be explained by concurrent disease or other drugs or chemicals. The response to the withdrawal of the drug (dechallenge) should be clinically plausible. The event must be definitive pharmacologically or phenomenologically, using a satisfactory rechallenge procedure if necessary.
- Probably related (PR) a reasonable time sequence to the administration of the drug, unlikely to be attributed to concurrent disease or other drugs or chemicals, and which follows a clinically reasonable response on withdrawal (dechallenge). Rechallenge information is not required to fulfill this definition.
- Possibly related (PO) a reasonable time sequence to administrations of the drug, but which could also be explained by concurrent disease or other drugs or chemicals. Information on drug withdrawal may be lacking or unclear.
- Unlikely related (UL) –a temporal relationship to drug administration which makes a causal relationship improbable, and in which other drugs, chemicals or underlying disease provide plausible explanations.
- Not related (NR) there is no evidence of a causal relationship between the study drug and the event and in which other drugs, chemicals or underlying disease explain the event.

Adverse events reported as definitely, probably, and possible, related to study therapy will be reported as related. In cases when the Investigator is unsure of the causality of an AE, the event will be considered related to study therapy unless deemed otherwise by the DSMC.

# 8.2.3 Expectedness

The Investigator will be responsible for determining whether or not an adverse event was expected or unexpected. Expected adverse events are those adverse events that are listed or characterized in the Package Insert (PI) or Reference Safety Information (RSI) of the current Investigator Brochure (IB). Unexpected adverse events are those not listed in the PI or current IB or not identified. This includes adverse events for which the specificity or severity is not consistent with the description in the PI or IB. For example, under this definition, hepatic necrosis would be unexpected if the PI or IB only referred to elevated hepatic enzymes or hepatitis.

# 8.2.4 Action Taken and Outcome

Start and stop dates will be required for all adverse events and serious adverse events. The action taken in response to the event should also be recorded in the subject's research chart and corresponding eCRF. Event action terms include none, medication administered, non-drug therapy administered, surgery, hospitalization, or other with the option to specify. If a new medication is added the medication should also be added to the concomitant medications log.

All adverse events should be followed until stabilization or resolution. Event outcomes may be classified as resolved, resolved with sequelae, ongoing, or death.

# 8.2.5 Reporting Serious Adverse Events

All serious adverse events should be reported as soon as possible but no later than one business day after the Investigator becomes aware. All SAEs must be reported via the HCI CTMS (OnCore) and submitted to [contact]. The HCI Clinical Site Monitor will in turn, submit the report to the Medical Monitor. The RCO will summarize and present all reported SAEs according to the Data and Safety Monitoring Plan at the monthly DSMC meeting.

At a minimum, initial SAE reports must include a description of the event, assessment of event causality, event grade, and the expectedness of the event. Although the Investigator may not know all the information at the time of the event, the available information should be reported. An SAE follow-up may be submitted at a later date once more information is known. It is required that follow-up reports be submitted until the SAE is resolved.

#### Follow-Up Information

It is recommended that follow-up reports be submitted as new information becomes available, however, a follow-up report should be submitted within 7 days of knowledge of event resolution. Follow-up information will be added to the SAE in OnCore and submitted to the DSMC via RCO.

# 8.2.6 FDA Notifications

Per 21 CRF 312.32 adverse events and serious adverse events will be reported on a MedWatch 3500A form to the FDA. Reportable events will be reported by the RCO according to the following guidelines:

# 8.2.6.1 MedWatch 3500A Reporting Guidelines

In addition to completing appropriate patient demographic (Section A) and suspect medication information (Section C & D), the report should include the following information within the Event Description (Section B.5) of the MedWatch 3500A form:

- Protocol number and title description
- Description of event, severity, treatment, and outcome if known
- Supportive laboratory results and diagnostics (Section B.6)
- Investigator's assessment of the relationship of the adverse event to each investigational product and suspect medication
- Expectedness of the event (i.e., expected or unexpected event).

8.2.6.2 FDA Reporting Timelines:

• 7 Calendar Day Report:

Any event that is fatal or life-threatening, unexpected, and definitely, probably or possibly related to study medication will be reported to the FDA by telephone or fax within seven calendar days of first learning of the event.

• 15 Calendar Day Report:

Any event that is serious, unexpected, and definitely, probably or possibly related to study medication will be reported to the FDA in an IND safety report within 15 calendar days of first learning of the event.

In accordance with 21 CFR 312.32, an Analysis of Similar Events should be included in the IND Safety Report. All safety reports previously filed by the investigator with the IND concerning similar events should be analyzed and the significance of the new report in light of the previous, similar reports commented on.

FDA fax number for IND Safety Reports:

Fax: [name]

# 8.2.7 IRB Notification

The University of Utah IRB requires any unanticipated problems that may increase the risk to research participants be promptly reported. All study-therapy related, unexpected adverse events whose nature, severity, or frequency is not consistent with either:

- The unknown or foreseeable risk of adverse events that are described in the protocol related-documents, such as the IRB-approved research protocol, applicable investigator brochure, the current IRB-approved informed consent document, and/or other relevant sources of information, such as product labeling and package inserts; or
- The expected natural progression of any underlying disease or condition of the subject(s) experiencing the adverse event.

Adverse events meeting this criterion must be promptly reported to the IRB within 10 business days of awareness.

## 8.2.8 Drug Manufacturer Notifications

SAEs, regardless of causal relationship, as outlined in section 8.1 must be reported to Repare Therapeutics within one (1) business day of the Investigator's knowledge of the event by submitting a completed SAE report form to [contact] and [contact].

All Serious Unexpected Serious Adverse Reactions (SUSAR) shall be submitted to Repare Therapeutics at least 4 calendar days prior to the safety report (7/15 Day Safety Reports) due date. SUSARS should be reported to [contact], [contact], and [contact].

#### 8.3 Special Situations

#### 8.3.1 Pregnancy or Breastfeeding

Although pregnancy is not considered an adverse event, any exposure to the investigational products during pregnancy or breastfeeding must be reported promptly. Exposure may occur by a woman actively receiving study therapy or the partner of a male subject actively receiving study therapy becomes pregnant. Any possible pregnancy or breastfeeding exposure during study therapy and up to 28 days after the last dose of study therapy or up to the start of subsequent anticancer therapy (whichever happens first) must be reported within one business day of awareness regardless of the occurrence of an SAE. Should a woman on study therapy become pregnant, she should immediately discontinue study treatment.

Women exposed to IP during pregnancy or while breastfeeding will be followed for pregnancy outcome and neonate health. Pregnancy outcomes may meet criteria as an SAE if ectopic pregnancy, spontaneous abortion, intrauterine fetal demise, neonatal death, or congenital anomaly occurs. Congenital anomalies that occur in a live-born baby, a terminated fetus, an intrauterine fetal demise, or a neonatal death should be reported as an SAE. Any neonatal deaths that occur up to 30 days after birth or breastfeeding exposure should be reported as an SAE. Further follow-up on birth outcomes and neonate health will be handled on a case-by-case base.

Pregnancies and any associated SAEs will be reported to Repare Therapeutics within one (1) business day of the Investigator's knowledge of the pregnancy.

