- 5.1.9 \_\_\_\_\_ Able to adhere to study visit schedule and other protocol requirements
- 5.1.10 \_\_\_\_\_ Patients must be able to swallow capsules

5.1.11 \_\_\_\_\_ Patients must be able to receive xanthine oxidase inhibitor and/or rasburicase for tumor lysis syndrome prophylaxis.

5.1.12 \_\_\_\_\_ Patients with a history of hepatitis B (surface antigen or core antibody-positive and PCR positive) must take lamivudine or equivalent drug during study therapy and for one year after completion of all therapy. Patients on IVIG who are core antibody-positive but PCR negative are not mandated to take prophylaxis.

5.1.13 \_\_\_\_\_ Patients who are HIV+ are eligible under the following circumstances:

- Undetectable HIV viral load (laboratory value obtained within the last 6 months prior to enrollment)
- CD4 count ≥200 (laboratory value obtained within the last 6 months prior to enrollment)
- Actively taking antiretroviral therapy (ART)
- Current ART therapy cannot have significant interactions with RP-3500 or Olaparib (Refer to Appendix 5). If current medications do interact, patients should receive alternative ART.

5.1.14 \_\_\_\_ Recovery to baseline or  $\leq$  Grade 1 CTCAE v5.0 from toxicities related to any prior cancer therapy, unless considered clinically not significant by the treating investigator.

5.1.15 \_\_\_\_\_ Female patients capable of reproduction or males who have partners capable of reproduction must agree to the use of an effective contraceptive method during the course of the study and for 6 months following the completion of their last treatment.

5.1.16 \_\_\_\_ Females of childbearing potential must have a negative serum  $\beta$ -Hcg pregnancy test result within 3 days of the first study dose. Female patients who are surgically sterilized or who are >45 years old and have not experienced menses for >2 years may have  $\beta$ -Hcg pregnancy test waived.

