### 5.4.2 Contraception

Due to the unknown abortifacient and teratogenic effects of RP-3500 and olaparib, a form of highly effective contraception is required for the duration of study therapy. Female subjects of childbearing potential must use a form of highly effective contraception from the start of study therapy until 6 months after the last dose of study therapy. Male subjects with a partner of childbearing potential must agree to use a method of highly effective contraception from the start of study therapy until 6 months after the last dose of study therapy.

Acceptable highly effective contraceptive methods include:

- Bilateral tubal occlusion
- Vasectomized partner
- Intra-uterine devise (IUD) or hormone-releasing system (IUS)
- Any hormonal (estrogen combined with progesterone or progesterone alone) contraception associated with inhibition of ovulation: implanted, oral, intravaginal, transdermal, or injectable.
- Spermicide with a compatible barrier method (i.e. diaphragm, sponge, or male or female condoms).
- Abstinence from heterosexual intercourse.

It is unknown whether RP-3500 and olaparib can produce drug transfer through seminal fluid. Therefore, male subjects must agree to use a condom during any form of intercourse from the start of study therapy until 6 months after the last dose of study therapy.

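### Pregnancy reporting in Section 8.3.1 stops at 28 days or less after the last dose, about five months before the contraception period ends, and conflicts with the section's own undated last sentence

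*Combined protocol and SAP*

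**What the plan says.** **Reporting.** Section 8.3.1 makes possible pregnancy or breastfeeding exposure reportable if it occurs on treatment and "up to 28 days after the last dose of study therapy or up to the start of subsequent anticancer therapy (whichever happens first"). The report is due within one business day of the site becoming aware. Exposed women are then followed for pregnancy outcome and the health of the newborn. The section ends with a separate instruction that carries no end date: "Pregnancies and any associated SAEs will be reported to Repare Therapeutics within one (1) business day of the" investigator learning of the pregnancy.

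**General safety window.** Section 8.2 has the same end point: "AEs and SAEs will be recorded from the initiation of study therapy until 28 days after the last dose of study medication". Starting another cancer treatment ends that window sooner.

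**Contraception.** Inclusion criterion 5.1.15 requires it during the study and "for 6 months following the completion of their last treatment". Section 5.4.2 says that women who could become pregnant "must use a form of highly effective contraception from the start of study therapy until 6 months after the last dose of study therapy". It sets the same period for men with a partner of childbearing potential. That section opens with the reason "Due to the unknown abortifacient and teratogenic effects of RP-3500 and olaparib". It adds that transfer through seminal fluid is unknown, and that for this reason "male subjects must agree to use a condom during any form of intercourse from the start of study therapy until 6 months", counted from the final dose.

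**The concern.** The protocol asks patients and their partners to avoid conception for six months after the last dose, but asks sites to report possible exposure for at most 28 of those days. If contraception fails in months two to six, the event falls inside the period in which the protocol wants conception avoided, yet no clear rule says that the site must report it or follow its outcome. If new anticancer therapy starts early, the reporting period is shorter still, although a new treatment does not undo an earlier exposure.

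What is at stake is safety information on a question that the protocol itself calls unknown. A fetal loss or congenital anomaly after a late conception would also fall outside the AE and SAE recording window in Section 8.2. Routine testing would not pick it up: the Schedule of Events (Section 1.3) plans a pregnancy test at screening, and later tests only as clinically indicated during treatment. Section 8.3.1 can also be read in two ways, so the two institutions named in Section 5.7 could apply it differently.

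**Working it through.** The plan states no figure on this point, so there is none to reproduce. The check compares time windows.

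**Inputs from the protocol**
- Reporting limit after the last dose: 28 days, or less if new therapy starts (8.3.1).
- Contraception after the last dose: 6 months (5.1.15, 5.4.2).
- Planned treatment: 18 cycles (Section 1.3, footnote 2) of 21 days (6.1). Treatment may continue beyond that (4.5.1).

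**Assumptions**
- Six months is 180 to 184 days.
- The date of new therapy is not given. Day 0 after the last dose is used as the extreme case.

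**Step 1. Post-dose gap** = six months − 28 days.
- 180 − 28 = 152 days, and 152/180 = 84.4%.
- 184 − 28 = 156 days, and 156/184 = 84.8%.
- With new therapy on day 0 the gap is the full 180 to 184 days (100%).

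**Step 2. Share of the whole contraception period** = gap / (treatment days + six months). For 18 cycles, treatment days = 18 × 21 = 378.
- 152/(378 + 180) = 152/558 = 27.2%.
- 156/(378 + 184) = 156/562 = 27.8%.
- New therapy on day 0: 180/558 = 32.3% to 184/562 = 32.7%.

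The same formula for shorter treatment:

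| Cycles | Treatment days | Uncovered, 28-day limit | Uncovered, new therapy on day 0 |
|---|---|---|---|
| 1 | 21 | 76% | 90% |
| 4 | 84 | 58% | 68–69% |
| 6 | 126 | 50% | 59% |
| 8 | 168 | 44% | 52% |
| 12 | 252 | 35–36% | 42% |
| 18 | 378 | 27–28% | 32–33% |

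**Step 3. Break-even.** The uncovered part is the larger part when the gap exceeds treatment days + 28.
- 152 − 28 = 124 days (5.9 cycles) to 156 − 28 = 128 days (6.1 cycles).
- With new therapy on day 0: 180/21 = 8.6 to 184/21 = 8.8 cycles.

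**Step 4. Does the last sentence of 8.3.1 close the gap?** It has no end date and could be read as covering any pregnancy the site hears of. But it concerns notification of the manufacturer only, and it comes after a paragraph that sets an explicit window. It does not extend outcome follow-up, which the section ties to women exposed to the product during pregnancy or breastfeeding. It therefore conflicts with the window and does not replace it.

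**The case against.** **An exposure window and a contraception period can differ.** Section 8.3.1 describes exposure as pregnancy in a woman on treatment or in the partner of a man on treatment. Section 3.7.2 gives an RP-3500 half-life of 2.7 to 23.0 hours, so 28 days (672 hours) is at least 672/23.0 = 29 half-lives. Section 5.4.2 links the unknown drug effects to contraception during therapy and gives no separate reason for the six-month extension for women. This has some force: calling the six months a risk period is an inference. But the protocol gives no olaparib half-life, it does tie the six-month condom rule to unknown seminal transfer, and it never states that the two windows differ on purpose.

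**The window limits when exposure occurs, not when it is discovered.** This stands. A pregnancy exposed within the window and found in month three is still reportable, and follow-up of exposed women has no 28-day limit. The gap concerns conceptions after the window.

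**The undated sentences may already cover late pregnancies.** The section's opening call for prompt reporting has no end date, nor does its last sentence. That supports calling the duty unclear instead of absent. It does not remove the conflict.

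**The new-therapy cut-off matches Section 8.2.** It does, and for adverse events that may be a sensible convention. It has no evident rationale for a pregnancy after earlier exposure.

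**Two stronger readings are tempting.** A reader might infer that most at-risk pregnancies go unreported. The documents do not support this. They give no pregnancy rates, contraception is mandatory throughout, time on treatment is fully covered, and the uncovered time is the larger part only for patients who stop before about 6 cycles (about 8.7 if new therapy starts at once). A reader might also infer that breastfeeding reporting should run to six months. Sections 5.1.15 and 5.4.2 concern contraception only, and breastfeeding appears as an entry exclusion (5.2.13) with no post-treatment period.

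**Conclusion.** The mismatch is real and unexplained. The reporting window ends 152 to 156 days before the contraception period does. About 85% of the post-dose contraception period, or 27 to 28% of the whole period for a patient who completes 18 cycles, has no clear duty to report a pregnancy or follow its outcome. Both shares are larger if new therapy starts within 28 days. They rest on counting six months as 180 to 184 days, and they measure time only.

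The practical yield is small. Section 4.4 plans 24 to 39 patients, and Section 3.5.1 gives a median age at diagnosis of 70, so few events are expected, although partners of male subjects also count. Pregnancies exposed during treatment, which are the most informative, are already reported and followed. No endpoint, sample size, error rate or dose decision is affected. This is a safety-reporting inconsistency that should be corrected because the correction is specific and cheap.

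**What to change.** Amend Section 8.3.1 as follows:

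- Define the end of pregnancy reporting by cross-reference to the contraception period in 5.1.15 and 5.4.2, so that the two cannot diverge again. Apply it to subjects and to partners of male subjects.
- Remove the start of subsequent anticancer therapy as a cut-off for pregnancies.
- State that outcome follow-up applies to every pregnancy reported in that period, and that associated SAEs are recorded despite the 28-day limit in Section 8.2.
- Give the closing sentence on manufacturer notification the same end date.
- Leave the breastfeeding window as it is. This evidence gives no reason to change it.

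The cost is a few sentences and a few more months of pregnancy reporting. Existing contacts can carry it: visits every 3 months in the first year after the last dose (Section 1.4) and, for patients who have progressed, survival contacts every 6 months (Sections 4.6 and 6.9.4). No new visit is needed, and the statistical analysis does not change.
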